11.1. Renal Insufficiency Analysis

The purpose of this analysis is to characterize the effect of renal impairment on the safety, and tolerability of simufilam.

Participants will be categorized into normal renal function or renal impairment groups based on their estimated glomerular filtration rate (eGFR) as shown in the table below.

Table 4: Renal Function Categories by eGFR Ranges

Renal Impairment ^a	Estimated eGFR (mL/min)
None (Normal)	≥ 90
Mild Renal Impairment	60 - 89
Moderate renal impairment	\geq 30 to <60
Severe Renal Impairment	≥15 to <30

a. Stages of renal impairment are based on Chronic Kidney Disease Epidemiology Collaboration (CKD-EPI) equation (2021) – for Adult Participants (≥ 18 years)

11.1.1 Calculation of eGFR:

The eGFR (in mL/min) will be calculated using the Chronic Kidney Disease Epidemiology Collaboration (CKD-EPI) equation (2021) − for Adult Participants (≥ 18 years):

$$eGFR = 142 \times [\min(S_{Cr}/k, 1)]^{\alpha} \times [\max(S_{Cr}/k, 1)]^{-1.200} \times 0.9938^{Age} \times 1.012 \ (if \ female)$$
 where

 S_{Cr} = standardized serum creatinine in mg/dL

k = 0.7 for females or 0.9 for males

 $\alpha = -0.241$ for females or -0.302 for males

[figure not shown]
min $(S_{Cr}/k, 1)$ is the minimum value of S_{Cr}/k or 1.0

max $(S_{Cr}/k, 1)$ is the maximum value of S_{Cr}/k or 1.0

age in years

As the Creatinine is collected at the visits; Day 1 (Baseline), Week 4, Week 16, Week 40, Week

Version 1.0 | 28-Feb-2025 Page 39 of 56

52. Week 64 and Week 76. eGFR will be calculated at the same visits.

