# 7.2. LABORATORY ASSESSMENTS

# 7.2.1. Clinical Laboratory Tests

The following clinical laboratory tests will be performed during the Screening Period, Baseline (Study Day 1) pre-dose, and at all follow-up visits:

- Hematology: white blood cell (WBC) count with differential, red blood cell (RBC) count, hemoglobin, hematocrit, platelet count.
- Serum Chemistry: glucose, sodium, potassium, chloride, bicarbonate, calcium, phosphate, blood urea nitrogen (BUN), total bilirubin, creatinine, albumin, globulin, total protein, uric acid, alkaline phosphatase (ALP), alanine transaminase (ALT), aspartate transaminase (AST), gamma glutamyl transpeptidase (GGT), lactose dehydrogenase (LDH).
- Urinalysis: color, specific gravity, pH, protein, glucose, ketones, occult blood, nitrites and leukocyte esterase. A "reflex" microscopic examination will be performed if protein, occult blood, nitrites or leukocyte esterase is present on the basic analysis.

• Screening Period: During the Screening Period only, bloods will be drawn for TSH, free T4, Vitamin B12, HepBsAg, HCV-Ab, HbA1C (diabetic subjects only) and plasma P-tau181 or P-tau217 (Note – plasma collection for P-tau181 or P-tau217 is not required if subject has documented evidence of AD pathophysiology prior to screening). The plasma P-tau181 test is a validated assay using ADX antibodies, which shows a wide dynamic range and an AUC of 0.92 during validation without any algorithms. Validation of a P-tau217 assay is pending. Urine to screen for drugs of abuse (amphetamines, cocaine, opiates and phencyclindine) will also be collected during the Screening Period.

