3.2.1. Safety Endpoints

The safety endpoints of this study include the following:

• Incidence of adverse events (AEs) including treatment-emergent, serious, related to study

Version 1.0 | 28-Feb-2025 Page 16 of 56

drug, and leading to withdrawal along with AEs by severity and relationship to study drug

- Mean change in clinical laboratory values from baseline to Weeks 4, 16, 28, 40, 52, 64 and 76. Shifts in the normality of clinical laboratory values from baseline to Weeks 4, 16, 28, 40, 52, 64 and 76.
- Mean change in vital signs (blood pressure [supine], temperature, pulse rate) from baseline to Weeks 4, 16, 28, 40, 52, 64 and 76.
- Mean change in body weight from baseline to Weeks 4, 16, 28, 40, 52, 64 and 76.
- Shifts in physical exam (PE) findings from baseline to Weeks 4, 16, 28, 40, 52, 64 and 76.
- Shifts in neurological exam (NE) findings from baseline to Weeks 4, 16, 28, 40, 52, 64 and 76.
- Mean change in ECG parameters from baseline to Weeks 4, 40 and 76.
- Concomitant medications/treatments usage
- Shifts in the C-SSRS from baseline to Weeks 4, 16, 28, 40, 52, 64 and 76.

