9.2. Clinical Laboratory Evaluations

The following clinical laboratory tests will be performed during the Screening Period, Baseline (Study Day 1) pre-dose, and at all follow-up visits (Week 4, Week 16, Week 28, Week 40, Week 52, Week 64, and Week 76/ET/ED).

Table 3: Protocol-Required Safety Laboratory Tests

Hematology							
Erythrocytes (RBC)	Eosinophils (EOS)	Leukocytes (WBC)					
Hemoglobin (HGB)	Lymphocytes (LYM)	Eosinophils/Leukocytes (EOSLE)					
Hematocrit (HCT)	Monocytes (MONO)	Lymphocytes/Leukocytes (LYMLE					
Platelets (PLAT)	Neutrophils (NEUT)	Monocytes/Leukocytes (MONOLE)					
Basophils (BASO)	Basophils/Leukocytes (BASOLE)	Neutrophils/Leukocytes (NEUTLE)					
Serum Chemistry							
Alanine aminotransferase (ALT)	Calcium (CA)	Phosphate (PHOS)					
Albumin (ALB)	Chloride (CL) Gamma-glutamyl transferase (GGT) Globulin (GLOBUL) Glucose (GLUC)	Potassium (K)					
Alkaline phosphatase (ALP)		Protein (PROT)					
Aspartate aminotransferase (AST)		Sodium (SODIUM)					
Bicarbonate (BICARB)	Creatinine (CREAT)	Urea Nitrogen (UREAN)					
Bilirubin (BILI)	Lactate dehydrogenase (LDH)	Urate (URATE)					
Urinalysis*							
Color (COLOR)	Leukocyte esterase (LEUKASE)	Protein (PROT)					
Glucose (GLUC)	Nitrite (NITRITE)	Specific gravity (SPGRAV)					
Ketones (KETONES)	рН (РН)	Occult Blood (OCCBLD)					

[figure not shown]
^{*} A "reflex" microscopic examination will be performed if protein, occult blood, nitrites, or leukocyte esterase is present on the basic analysis.

Screening Period: During the Screening Period only, bloods will be drawn for TSH, free T4, Vitamin B12, HepBsAg, HCV-Ab, HbA1C (diabetic participants only) and plasma P-tau181 (Note – plasma collection for P-tau181 not required if participant has documented evidence of AD pathophysiology prior to screening). Urine to screen for drugs of abuse (amphetamines, cocaine, opiates and phencyclindine) will also be collected during the Screening Period.

All hematology, chemistry, and urinalysis laboratory results will be presented in SI units, if available. Only laboratory parameters in the Table 3, will be tabulated.

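### SAP 11.1.1 leaves Week 28 out of the creatinine and eGFR visit list, and Table 4 leaves some eGFR values without a category

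*SAP*

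**What the plan says.** **Visits.** SAP 11.1.1 reads "As the Creatinine is collected at the visits; Day 1 (Baseline), Week 4, Week 16, Week 40, Week" and continues over the page break "52. Week 64 and Week 76. eGFR will be calculated at the same visits". That is Day 1 plus six post-baseline visits.

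The other sections give seven:
- SAP 9.2 schedules laboratory tests "at all follow-up visits (Week 4, Week 16, Week 28, Week 40, Week 52, Week 64, and Week 76/ET/ED", and its Table 3 lists "Creatinine (CREAT" in the serum chemistry panel.
- SAP 3.2.1 names as a safety endpoint "Mean change in clinical laboratory values from baseline to Weeks 4, 16, 28, 40, 52, 64 and 76".
- Protocol 7.2.1 has chemistry at "Baseline (Study Day 1) pre-dose, and at all follow-up visits". Protocol 7.1.6 (the Week 28 and 52 visits) and the Appendix A schedule agree.
- SAP Table 9 titles the renal figures 14.6.1.1 and 14.6.1.2 as covering each post-baseline visit.

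**Categories.** SAP Table 4 sets normal renal function at 90 or above. The "Mild Renal Impairment" row is 60 to 89, moderate is at least 30 and below 60, and severe is at least 15 and below 30. There is no lower row and no eGFR rounding rule. Section 11.1.2.2 uses renal function at baseline (Day 1) to group the treatment-emergent adverse event (TEAE) summaries.

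**The concern.** Two drafting faults sit in the same short section.

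First, the visit list states something about data collection that the rest of the SAP and the protocol contradict, and then makes the eGFR calculation depend on it. A programmer who follows 11.1.1 computes no eGFR at Week 28, which leaves a 24-week interval (Week 16 to Week 40) in the renal by-visit outputs. One who follows the figure titles does compute it.

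Second, the CKD-EPI formula in 11.1.1 returns a continuous value, but Table 4 mixes a whole-number range (60 to 89) with continuous limits (for example, at least 30 and below 60). The stated purpose of 11.1 is to describe how renal impairment affects safety and tolerability, so the grouping should place every participant in exactly one row. As printed, it does so only under a rounding convention that the reader must supply.

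**Working it through.** **1. Visit list.**

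| Source | Post-baseline visits |
|---|---|
| SAP 11.1.1 | 4, 16, 40, 52, 64, 76 (six) |
| SAP 9.2, SAP 3.2.1, protocol 7.2.1 and Appendix A | 4, 16, 28, 40, 52, 64, 76 (seven) |

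The difference is exactly Week 28: 1/7 = 14.3% of the post-baseline visits. This is not an extraction fault, because the page break falls after Week 40, whereas Week 28 would stand before it. SAP Table 2.1 also provides a Week 28 analysis window (Days 156 to 239), so nothing in the windowing explains the omission.

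**2. Whether ordinary values fall between 89 and 90.** The SAP's formula is eGFR = 142 × min(SCr/k, 1)^α × max(SCr/k, 1)^−1.200 × 0.9938^age (× 1.012 if female), with k = 0.9 and α = −0.302 for men, and k = 0.7 and α = −0.241 for women.

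- Man aged 75, creatinine 0.90 mg/dL: SCr/k = 1, so eGFR = 142 × 0.9938^75 = 89.07, which has no category. Creatinine of 0.87, 0.88 and 0.89 gives 89.98, 89.67 and 89.37, also unassigned.
- Woman aged 80, creatinine 0.62, 0.63 and 0.64 mg/dL: 89.97, 89.62 and 89.28, all unassigned.

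Over the eligible ages 50 to 87, with creatinine in steps of 0.01 mg/dL, 60 combinations for men and 53 for women (113 in all) fall strictly between 89 and 90.

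**3. How many participants.** The documents give no eGFR distribution. Assume baseline eGFR is normal with mean μ and SD σ. The share in the gap is Φ((90 − μ)/σ) − Φ((89 − μ)/σ), applied to the planned 1083.

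| μ | σ = 12 | σ = 15 | σ = 18 |
|---|---|---|---|
| 70 | 0.89% (9.6) | 1.14% (12.4) | 1.23% (13.3) |
| 75 | 1.60% (17.4) | 1.67% (18.1) | 1.60% (17.4) |
| 80 | 2.43% (26.3) | 2.18% (23.6) | 1.93% (20.9) |
| 85 | 3.10% (33.6) | 2.54% (27.5) | 2.15% (23.3) |

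This applies only if eGFR is left unrounded. Rounded to whole numbers, every value becomes 89 or 90 and the count in the gap is 0.

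**4. Values below 15.** At ages 50 to 87 the formula falls below 15 only when creatinine exceeds about 3.7 to 4.5 mg/dL in men or 2.9 to 3.6 mg/dL in women. Under the same assumed distributions the expected baseline count is between 0 and 1.2 of 1083, before any exclusion criterion is applied.

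**5. Whether rounding is a harmless choice.** It also moves people at the 60 boundary. A man aged 70 with creatinine 1.29 mg/dL has eGFR 142 × (1.29/0.9)^−1.200 × 0.9938^70 = 59.65: moderate if unrounded, mild if rounded. With mean 70 to 80 and SD 15, about 0.5 to 1.1% of 1083 (about 6 to 11 participants) lie between 59.5 and 60.

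**The case against.** The strongest reply on visits is that the sentence in 11.1.1 is a slip in describing when creatinine is collected, and not a decision to drop a visit. Section 11.1.2.1 runs the summaries through Week 76, tables 14.5.1.1 and 14.5.1.2 are by visit, and the figures are for each post-baseline visit. That is probably right about intent. But 11.1.1 is the only place that says when eGFR is calculated, and it conflicts with those titles, so the text still needs correcting.

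On categories, the reply is that a row of 60 to 89 suggests whole-number eGFR, which empties the gap. That is a reasonable reading, but the SAP does not state it and the two rows below use continuous limits. The reply on the missing bottom row is largely sound: protocol exclusions 41 and 42 remove clinically significant laboratory abnormalities and unstable, clinically significant renal disease, so a baseline eGFR below 15 is very unlikely. A post-baseline value remains possible.

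A reader might infer three stronger things that the documents do not support:
- *That renal information between Weeks 16 and 40 is lost.* Creatinine is in the general chemistry panel, is summarised with change from baseline under SAP 9.2 (table 14.3.5.1.1), and falls under the Week 28 laboratory endpoint in 3.2.1.
- *That the Week 28 omission weakens the TEAE-by-renal-function tables.* Those use baseline renal function only.
- *That participants are certain to disappear from the tables.* That depends on rounding, and anyone unclassified would still be in the main TEAE, serious adverse event and laboratory tables.

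**Conclusion.** Both faults are real and minor. Read literally, 11.1.1 removes one of seven post-baseline visits from the renal by-visit creatinine and eGFR outputs, and from nothing else. Table 4 is not exhaustive for a continuous eGFR. In the baseline renal-function and TEAE-by-renal-function tables, the 89 to 90 gap leaves about 10 to 34 of 1083 participants unclassified (about 1 to 3%) if eGFR is unrounded, and none if it is rounded to whole numbers. Few or none are expected below 15 at baseline. The range rests on an assumed normal distribution (mean 70 to 85, SD 12 to 18) and on the planned enrolment; neither the true distribution nor the rounding convention is in the documents. The analysis is descriptive and supplementary. Alpha, power and the co-primary analyses are untouched.

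**What to change.** In SAP 11.1.1, add Week 28 to the creatinine and eGFR visit list, so that it matches 9.2, 3.2.1, the protocol schedule and the renal figure titles. In Table 4, state that categories are assigned on unrounded eGFR and define them as ≥ 90, ≥ 60 to < 90, ≥ 30 to < 60, ≥ 15 to < 30, and < 15. The cost is a few lines of SAP text. No new data are needed, because creatinine is already scheduled at Week 28.

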11.1.2 Statistical Methods and Analysis

11.1.2.1 Statistical Summaries on Creatinine, eGFR and Renal Function

The descriptive statistics of the observed and the change from baseline in Creatinine will be summarized by treatment group and renal function through Week 76. The same information will be graphically displayed using a clustered bar chart.

The descriptive summary statistics of eGFR will be presented by treatment group and renal function through Week 76.

The number of participants and percentages of renal function will be presented for the subgroups; MMSE (16-20, 21-27), age (>=75, 65-74, and < 65), sex, and ethnicity, by treatment group at Baseline (Day 1).

11.1.2.2 Statistical Summaries on Select TEAEs vs Renal Function at Baseline (Day 1)

The effect of renal impairment on TEAEs will be characterized by displaying the summary statistics as well as the plots.

A summary of TEAEs by relatedness and renal function derived at Baseline (Day 1) will be provided by treatment groups.

A summary of select TEAEs Incidence by Renal Function derived at Baseline (Day 1) will be provided along with a clustered bar plot, where the select TEAEs of interest (Preferred Terms of the 10 most frequent TEAEs at the end of the study) when assessing the impact of study drug according to renal function.

13.1. Demographic Data Summary Tables and Figures

Table 5: Demographic Data Summary Tables and Figures

Table Number	Population	Table Title/Summary
14.1.1	All Subjects	Subject Disposition (Includes All Early Terminations)
14.1.2.1.1	ITT	Demographics and Baseline Characteristics
14.1.2.1.2	ITT-mild	Demographics and Baseline Characteristics
14.1.2.1.3	mITT	Demographics and Baseline Characteristics
14.1.2.2	Safety	Demographics and Baseline Characteristics
14.1.2.3.1	ITT	Medical History
14.1.2.3.2	ITT-mild	Medical History
14.1.2.4.1.1	ITT	Prior Medications
14.1.2.4.1.2	ITT-mild	Prior Medications
14.1.3.1	Safety	Study Drug Exposure
14.1.3.2	Safety	Study Drug Compliance by Visit
14.1.4.1	ITT	Important Protocol Deviations
14.1.4.2	ITT-mild	Important Protocol Deviations

13.2. Efficacy Data

Table 6: Efficacy Data

Table Number	Population	Table Title/Summary
T14.2.1	mITT	Summary of Primary, Secondary, and Exploratory Endpoints- Primary Efficacy Model
T14.2.1.1.1	mITT	Summary of Change from Baseline to Week 76 in ADAS-Cog 12 Total Score by Visit and Treatment
T14.2.1.2.1	ITT	Summary of Change from Baseline to Week 76 in ADAS-Cog 12 Total Score by Visit and Treatment
T14.2.1.3.1	cITT	Summary of Change from Baseline to Week 76 in ADAS-Cog 12 Total Score by Visit and Treatment
T14.2.1.4.1	ITT-mild	Summary of Change from Baseline to Week 76 in ADAS-Cog 12 Total Score by Visit and Treatment
T14.2.1.1.2	mITT	Summary of Change from Baseline to Week 76 in ADAS-Cog 12 Total Score by Visit and Treatment: Imputation Missing Not at Random
T14.2.1.1.3	mITT	Summary of Change from Baseline to Week 76 in ADAS-Cog 12 Total Score by Visit and Treatment; Post Baseline Dose Change or Concomittant Medication Censoring Sensitivity Analysis
T14.2.1.1.4	mITT	Summary of Change from Baseline to Week 76 in ADAS-Cog 12 Total Score by Visit and Treatment; Intercurrent Event Sensitivity analysis

Version 1.0 | 28-Feb-2025 Page 41 of 56

T14.2.1.5.1	mITT amnestic subset	Summary of Change from Baseline to Week 76 in ADAS-Cog 12 Total Score by Visit and Treatment
T14.2.1.2.6	ITT	Summary of Change from Baseline to Week 76 in ADAS-Cog 12 Total Score by Visit and Treatment Stratified by Mild (21-27)/Moderate(<21) AD Status
T14.2.1.2.7	ITT	Summary of Change from Baseline to Week 76 in ADAS-Cog 12 Total Score by Visit and Treatment Stratified by MMSE Total Score ≥20 and ≤27
T14.2.1.2.8	ITT	Summary of Change from Baseline to Week 76 in ADAS-Cog 12 Total Score by Visit and Treatment Stratified by Age Group
T14.2.1.2.9	ITT	Summary of Change from Baseline to Week 76 in ADAS-Cog 12 Total Score by Visit and Treatment Stratified by Sex
T14.2.1.2.10	ITT	Summary of Change from Baseline to Week 76 in ADAS-Cog 12 Total Score by Visit and Treatment Stratified by Race
T14.2.1.2.11	ITT	Summary of Change from Baseline to Week 76 in ADAS-Cog 12 Total Score by Visit and Treatment Stratified by Ethnicity
T14.2.1.2.12	ITT	Summary of Change from Baseline to Week 76 in ADAS-Cog 12 Total Score by Visit and Treatment Stratified by ApoE4 Genotype
T14.2.1.2.13	ITT	Summary of Change from Baseline to Week 76 in ADAS-Cog 12 Total Score by Visit and Treatment Stratified by Medication Usage
T14.2.1.2.14	ITT	Summary of Change from Baseline to Week 76 in ADAS-Cog 12 Total Score by Visit and Treatment Stratified by Baseline Severity Group
T14.2.1.2.15	ITT	Summary of Change from Baseline to Week 76 in ADAS-Cog 12 Total Score by Visit and Treatment Stratified by Baseline Plasma P-Tau 181 Level
T14.2.1.2.16	ITT	Summary of Change from Baseline to Week 76 in ADAS-Cog 12 Total Score by Visit and Treatment: Responder Analysis
T14.2.1.2.17	ITT	Summary of Change from Baseline to Week 76 in ADAS-Cog 12 Total Score by Visit and Treatment Mild (21-27)/Moderate(<21) AD Status: Responder Analysis
T14.2.1.2.18	ITT	Summary of Change from Baseline to Week 76 in ADAS-Cog 12 Total Score by Visit and Treatment: Mild to Moderate Progression Analysis
T14.2.1.2.19	ITT	Summary of Change from Baseline to Week 76 in ADAS-Cog 12 Total Score by Visit and Treatment: Moderate to Severe Progression Analysis
T14.2.1.2.20	ITT	Summary of Change from Baseline to Week 76 in ADAS-Cog 12 Total Score by Visit and Treatment: Time Component Test
T14.2.1.6.1	Pooled	Summary of Change from Baseline to Week 52 in ADAS-Cog 12 Total Score by Visit and Treatment
T14.2.1.6.2	Pooled	Summary of Change from Baseline to Week 52 in ADAS-Cog 12 Total Score by Visit and Treatment Stratified by Baseline Severity Group
T14.2.1.6.3	Pooled	Summary of Change from Baseline to Week 52 in ADAS-Cog 12 Total Score by Visit and Treatment Stratified by Baseline Plasma P-Tau Level
T14.2.2.1.1	mITT	Summary of Change from Baseline to Week 76 in ADCS-ADL Total Score by Visit and Treatment
T14.2.2.2.1	ITT	Summary of Change from Baseline to Week 76 in ADCS-ADL Total Score by Visit and Treatment
T14.2.2.3.1	cITT	Summary of Change from Baseline to Week 76 in ADCS-ADL Total Score by Visit and Treatment
T14.2.2.4.1	ITT-mild	Summary of Change from Baseline to Week 76 in ADCS-ADL Total Score by Visit and Treatment

Version 1.0 | 28-Feb-2025 Page 42 of 56

T142212	ITT	Summary of Change from Baseline to Week 76 in ADCS-ADL Total
T14.2.2.1.2	mITT	Score by Visit and Treatment: Imputation Missing Not at Random
T14.2.2.1.3	mITT	Summary of Change from Baseline to Week 76 in ADCS-ADL Total Score by Visit and Treatment; Post Baseline Dose Change or Concomittant Medication Censoring Sensitivity Analysis
T14.2.2.1.4	mITT	Summary of Change from Baseline to Week 76 in ADCS-ADL Total Score by Visit and Treatment; Intercurrent Event Sensitivity analysis
T14.2.2.5.1	mITT amnestic subset	Summary of Change from Baseline to Week 76 in ADCS-ADL Total Score by Visit and Treatment
T14.2.2.2.6	ITT	Summary of Change from Baseline to Week 76 in ADCS-ADL Total Score by Visit and Treatment Stratified by Mild (21-27)/Moderate(<21) AD Status
T14.2.2.2.7	ITT	Summary of Change from Baseline to Week 76 in ADCS-ADL Total Score by Visit and Treatment Stratified by MMSE Total Score ≥20 and ≤27
T14.2.2.2.8	ITT	Summary of Change from Baseline to Week 76 in ADCS-ADL Total Score by Visit and Treatment Stratified by Age Group
T14.2.2.2.9	ITT	Summary of Change from Baseline to Week 76 in ADCS-ADL Total Score by Visit and Treatment Stratified by Sex
T14.2.2.2.10	ITT	Summary of Change from Baseline to Week 76 in ADCS-ADL Total Score by Visit and Treatment Stratified by Race
T14.2.2.2.11	ITT	Summary of Change from Baseline to Week 76 in ADCS-ADL Total Score by Visit and Treatment Stratified by Ethnicity
T14.2.2.2.12	ITT	Summary of Change from Baseline to Week 76 in ADCS-ADL Total Score by Visit and Treatment Stratified by ApoE4 Genotype
T14.2.2.2.13	ITT	Summary of Change from Baseline to Week 76 in ADCS-ADL Total Score by Visit and Treatment Stratified by Medication Usage
T14.2.2.2.14	ITT	Summary of Change from Baseline to Week 76 in ADCS-ADL Total Score by Visit and Treatment Stratified by Baseline Severity Group
T14.2.2.2.15	ITT	Summary of Change from Baseline to Week 76 in ADCS-ADL Total Score by Visit and Treatment Stratified by Baseline Plasma P-Tau 181 Level
T14.2.2.2.16	ITT	Summary of Change from Baseline to Week 76 in ADCS-ADL Total Score by Visit and Treatment: Responder Analysis
T14.2.2.2.17	ITT	Summary of Change from Baseline to Week 76 in ADCS-ADL Total Score by Visit and Treatment Mild (21-27)/Moderate(<21) AD Status: Responder Analysis
T14.2.2.2.18	ITT	Summary of Change from Baseline to Week 76 in ADCS-ADL Total Score by Visit and Treatment: Mild to Moderate Progression Analysis
T14.2.2.2.19	ITT	Summary of Change from Baseline to Week 76 in ADCS-ADL Total Score by Visit and Treatment: Moderate to Severe Progression Analysis
T14.2.2.2.20	ITT	Summary of Change from Baseline to Week 76 in ADCS-ADL Total Score by Visit and Treatment: Time Component Test
T14.2.2.6.1	Pooled	Summary of Change from Baseline to Week 52 in ADCS-ADL Total Score by Visit and Treatment
T14.2.2.6.2	Pooled	Summary of Change from Baseline to Week 52 in ADCS-ADL Total Score by Visit and Treatment Stratified by Baseline Severity Group
T14.2.2.6.3	Pooled	Summary of Change from Baseline to Week 52 in ADCS-ADL Total Score by Visit and Treatment Stratified by Baseline Plasma P-Tau Level
T14.2.3.1.1	mITT	Summary of Change from Baseline to Week 76 in iADRS Total Score by Visit and Treatment

Version 1.0 | 28-Feb-2025 Page 43 of 56

T14.2.3.2.1	ITT	Summary of Change from Baseline to Week 76 in iADRS Total Score by Visit and Treatment
T14.2.3.3.1	cITT	Summary of Change from Baseline to Week 76 in iADRS Total Score by Visit and Treatment
T14.2.3.4.1	ITT-mild	Summary of Change from Baseline to Week 76 in iADRS Total Score by Visit and Treatment
T14.2.3.5.1	mITT amnestic subset	Summary of Change from Baseline to Week 76 in iADRS Total Score by Visit and Treatment
T14.2.3.2.6	ITT	Summary of Change from Baseline to Week 76 in iADRS Total Score by Visit and Treatment Stratified by Mild (21-27)/Moderate(<21) AD Status
T14.2.3.2.7	ITT	Summary of Change from Baseline to Week 76 in iADRS Total Score by Visit and Treatment Stratified by MMSE Total Score ≥20 and ≤27
T14.2.3.2.8	ITT	Summary of Change from Baseline to Week 76 in iADRS Total Score by Visit and Treatment Stratified by Age Group
T14.2.3.2.9	ITT	Summary of Change from Baseline to Week 76 in iADRS Total Score by Visit and Treatment Stratified by Sex
T14.2.3.2.10	ITT	Summary of Change from Baseline to Week 76 in iADRS Total Score by Visit and Treatment Stratified by Race
T14.2.3.2.11	ITT	Summary of Change from Baseline to Week 76 in iADRS Total Score by Visit and Treatment Stratified by Ethnicity
T14.2.3.2.12	ITT	Summary of Change from Baseline to Week 76 in iADRS Total Score by Visit and Treatment Stratified by ApoE4 Genotype
T14.2.3.2.13	ITT	Summary of Change from Baseline to Week 76 in iADRS Total Score by Visit and Treatment Stratified by Medication Usage
T14.2.3.2.14	ITT	Summary of Change from Baseline to Week 76 in iADRS Total Score by Visit and Treatment Stratified by Baseline Severity Group
T14.2.3.2.15	ITT	Summary of Change from Baseline to Week 76 in iADRS Total Score by Visit and Treatment Stratified by Baseline Plasma P-Tau 181 Level
T14.2.3.6.1	Pooled	Summary of Change from Baseline to Week 52 in iADRS Total Score by Visit and Treatment
T14.2.3.6.2	Pooled	Summary of Change from Baseline to Week 52 in iADRS Total Score by Visit and Treatment Stratified by Baseline Severity Group
T14.2.3.6.3	Pooled	Summary of Change from Baseline to Week 52 in iADRS Total Score by Visit and Treatment Stratified by Baseline Plasma P-Tau Level
T14.2.4.1.1	mITT	Summary of Change from Baseline to Week 76 in MMSE Total Score by Visit and Treatment
T14.2.4.2.1	ITT	Summary of Change from Baseline to Week 76 in MMSE Total Score by Visit and Treatment
T14.2.4.3.1	cITT	Summary of Change from Baseline to Week 76 in MMSE Total Score by Visit and Treatment
T14.2.4.4.1	ITT-mild	Summary of Change from Baseline to Week 76 in MMSE Total Score by Visit and Treatment
T14.2.4.6.1	Pooled	Summary of Change from Baseline to Week 52 in MMSE Total Score by Visit and Treatment
T14.2.4.6.2	Pooled	Summary of Change from Baseline to Week 52 in MMSE Total Score by Visit and Treatment Stratified by Baseline Severity Group
T14.2.4.6.3	Pooled	Summary of Change from Baseline to Week 52 in MMSE Total Score by Visit and Treatment Stratified by Baseline Plasma P-Tau Level
T14.2.5.1.1	mITT	Summary of Change from Baseline to Week 76 in NPI-10 Total Score by Visit and Treatment

Version 1.0 | 28-Feb-2025 Page 44 of 56

T14.2.5.2.1	ITT	Summary of Change from Baseline to Week 76 in NPI-10 Total Score by Visit and Treatment
T14.2.5.3.1	cITT	Summary of Change from Baseline to Week 76 in NPI-10 Total Score by Visit and Treatment
T14.2.5.4.1	ITT-mild	Summary of Change from Baseline to Week 76 in NPI-10 Total Score by Visit and Treatment
T14.2.5.5.1	ITT	Summary of Change from Baseline to Week 76 in NPI-10 Total Score by Visit and Treatment in Participants with a baseline NPI-10 Score ≥2
T14.2.5.6.1	ITT	Summary of Change from Baseline to Week 76 in NPI-10 Agitation and Aggression Domain Scores by Visit and Treatment in Participants with a Non-Zero Baseline Score for that Domain
T14.2.5.7.1	ITT	Summary of Change from Baseline to Week 76 in NPI-10 Total Score by Visit and Treatment: Responder Analysis
T14.2.5.6.1	Pooled	Summary of Change from Baseline to Week 52 in NPI-10 Total Score by Visit and Treatment
T14.2.5.6.2	Pooled	Summary of Change from Baseline to Week 52 in NPI-10 Total Score by Visit and Treatment Stratified by Baseline Severity Group
T14.2.5.6.3	Pooled	Summary of Change from Baseline to Week 52 in NPI-10 Total Score by Visit and Treatment Stratified by Baseline Plasma P-Tau Level
T14.2.6.1.1	mITT	Summary of Change from Baseline to Week 76 in ZBI Total Score by Visit and Treatment
T14.2.6.2.1	ITT	Summary of Change from Baseline to Week 76 in ZBI Total Score by Visit and Treatment
T14.2.6.3.1	cITT	Summary of Change from Baseline to Week 76 in ZBI Total Score by Visit and Treatment
T14.2.6.4.1	ITT-mild	Summary of Change from Baseline to Week 76 in ZBI Total Score by Visit and Treatment
T14.2.6.6.1	Pooled	Summary of Change from Baseline to Week 52 in ZBI Total Score by Visit and Treatment
T14.2.6.6.2	Pooled	Summary of Change from Baseline to Week 52 in ZBI Total Score by Visit and Treatment Stratified by Baseline Severity Group
T14.2.6.6.3	Pooled	Summary of Change from Baseline to Week 52 in ZBI Total Score by Visit and Treatment Stratified by Baseline Plasma P-Tau Level
T14.2.7.1.1	mITT	Summary of Change from Baseline to Week 76 in CDR-SB Total Score by Visit and Treatment
T14.2.7.2.1	ITT	Summary of Change from Baseline to Week 76 in CDR-SB Total Score by Visit and Treatment
T14.2.7.3.1	cITT	Summary of Change from Baseline to Week 76 in CDR-SB Total Score by Visit and Treatment
T14.2.7.4.1	ITT-mild	Summary of Change from Baseline to Week 76 in CDR-SB Total Score by Visit and Treatment
T14.2.7.6.1	Pooled	Summary of Change from Baseline to Week 52 in CDR-SB Total Score by Visit and Treatment
T14.2.7.6.2	Pooled	Summary of Change from Baseline to Week 52 in CDR-SB Total Score by Visit and Treatment Stratified by Baseline Severity Group
T14.2.7.6.3	Pooled	Summary of Change from Baseline to Week 52 in CDR-SB Total Score by Visit and Treatment Stratified by Baseline Plasma P-Tau Level
T14.2.8.1.1	ITT-plasma	Summary of Change from Baseline to week 76 in Plasma P-Tau 217 by Visit and Treatment
T14.2.8.1.2	ITT-CSF	Summary of Change from Baseline to week 76 in CSF P-Tau 217 by Visit and Treatment
	•	

Version 1.0 | 28-Feb-2025 Page 45 of 56

T14.2.9.1.1	ITT-plasma	Summary of Change from Baseline to week 76 in Plasma Total Tau by Visit and Treatment
T14.2.9.1.2	ITT-CSF	Summary of Change from Baseline to week 76 in CSF Total Tau by Visit and Treatment
T14.2.10.1.1	ITT-plasma	Summary of Change from Baseline to week 76 in Plasma GFAP by Visit and Treatment
T14.2.10.1.2	ITT-CSF	Summary of Change from Baseline to week 76 in CSF GFAP by Visit and Treatment
T14.2.11.1.1	ITT-plasma	Summary of Change from Baseline to week 76 in Plasma NfL by Visit and Treatment
T14.2.11.1.2	ITT-CSF	Summary of Change from Baseline to week 76 in CSF NfL by Visit and Treatment
T14.2.12.1.1	PET	Summary of Change from Baseline to week 76 in tau PET by Visit and Treatment
T14.2.12.1.2	PET	Summary of Change from Baseline to week 76 in amyloid PET by Visit and Treatment
T14.2.13.1.1	MRI	Summary of Change from Baseline to week 76 in Whole Brain Volume by Visit and Treatment
T14.2.13.1.2	MRI	Summary of Change from Baseline to week 76 in Ventricular Volume by Visit and Treatment
T14.2.14.1.1	MRI	Summary of Change from Baseline to week 76 in Hippocampal Volume by Visit and Treatment
T14.2.14.1.2	MRI	Summary of Change from Baseline to week 76 in Cortical Thickness Volume by Visit and Treatment

